Alcohol exerts a significant suppressive effect on the immune system, which leads to a vulnerability to a wide array of infections, especially pneumonia. Studies in various organ systems have consistently demonstrated that alcohol abuse impairs the clearance of infectious organisms⁹ resulting in 1) an increased risk for community-acquired and nosocomial pneumonia, 2) higher hospitalization-associated charges, 3) higher intensive care unit use and longer inpatient stays¹⁰, and 4) higher mortality rates.¹¹ Alcohol abuse has a longstanding link with pulmonary infections, and in a recent study of patients admitted to a general hospital with pneumonia, 25-50% of such individuals were found to have a concomitant diagnosis of alcoholism.^{12,13} Moreover, these alcoholic patients were more likely to be infected with serious Gram-negative bacteria such as *Klebsiella pneumoniae*.¹⁴ Despite this longstanding awareness, a detailed understanding of the mechanisms responsible for predisposing alcoholics to lung infections is lacking and may be the key to uncovering new intervention strategies that could reduce morbidity and mortality in these vulnerable subjects.

The alveolar macrophage plays a key role in protecting the individual from developing pneumonia. The increased risk of pneumonia in the alcoholic host involves at least three important factors: 1) colonization of the oropharynx with pathogenic bacteria, which occurs in approximately one-third of alcoholics; 2) increased frequency of aspiration as a result of depressed level of consciousness and diminished gag and cough reflexes; and 3) impaired integrity of the host immune system.¹⁵ A crucial element of host defense in the lung is the alveolar macrophage. The lung is constantly exposed to the outside world, and the first cellular line of defense in protecting the alveolar space from invading pathogens is the resident macrophage. It is the primary phagocyte on the gas exchange surface of the lung and normally has the capacity to efficiently ingest and destroy inhaled pathogens. However, clinical and laboratory studies have identified that alveolar macrophages are impaired by chronic alcohol

ingestion. For example, we determined that alveolar macrophages isolated from rats on a chronic alcohol diet have significantly impaired immune function and are poorly equipped to phagocytose bacteria.¹⁶ Therefore, alveolar macrophage immune dysfunction is clearly implicated in the link between chronic alcohol consumption and the increased risk of pulmonary infections.

Oxidative stress is a fundamental feature of the alcoholic lung phenotype and interferes with the function of numerous cell types including the alveolar macrophage. Our research group has identified in clinical and animal studies that chronic alcohol ingestion depletes the alveolar lining fluid levels of glutathione (GSH), a critical antioxidant, by ~80% and oxidizes the redox potential by 35-50 mV.¹⁷⁻¹⁹ Further investigations determined that alcohol-induced oxidant stress impaired alveolar macrophage terminal differentiation and plasma membrane expression of the receptors necessary to drive phagocytosis and the respiratory burst.^{16, 19-21} More importantly, oral GSH precursors attenuated the alcohol-induced oxidant stress and improved AM immune functions in animal models.^{19, 22} These findings suggest that dietary supplements that restore GSH availability within the alveolar space could improve alveolar macrophage immune function in alcoholics, although the potential benefit of this therapeutic modality has yet to be tested in clinical studies.

The essential micronutrient zinc is crucial for normal immune function, and it is deficient in alcoholics. A key participant in normal host immune response is zinc, a trace element that is critical for normal protein metabolism, the function of more than 300 zinc metalloenzymes, and for membrane integrity.²³⁻²⁵ Alcoholics are prone to numerous nutritional deficiencies as the result of poor dietary intake, and zinc deficiency has long been recognized in this context. Zinc deficiency in the healthy, non-alcoholic population is uncommon in the United States, but contributes to a significant burden of disease in other parts of the world such as sub-Saharan Africa and Southeast Asia where dietary intake is severely limited²⁶ and where children in particular are at high risk of pneumonia.²⁷ Consistent with this association, there is evolving evidence that zinc is critical to airway health.^{23, 25, 28, 29} Importantly, even though there has been considerable attention to examining how alcohol-related zinc deficiency affects the liver, the important role of zinc deficiency in mediating the alcoholic lung phenotype has only been recently recognized in our animal studies.^{30, 31} Furthermore, we have preliminary data showing that human alcoholics show evidence of zinc deficiency in the alveolar space, and the next logical step would be to explore the potential role of zinc therapy in these patients.

Despite the overwhelming evidence for zinc deficiency and oxidative stress in the alcoholic population, there are no trials evaluating the lung health effects of either dietary zinc or antioxidant supplementation in humans who abuse alcohol. If either of these strategies is able to reverse the immune dysfunction seen in the setting of chronic alcohol consumption, it offers a potentially simple therapeutic option for this high risk population.

2. Objectives

2.1 Primary Aim

ExZACTO is a four-arm (1:1:1:1), factorial design, placebo-controlled, double-blind randomized clinical trial. The study is a clinical intervention trial that will determine the impact of both dietary zinc supplementation and dietary S-adenosylmethionine (SAME) supplementation, individually and in combination, on alveolar macrophage immune function, intracellular zinc levels in the alveolar macrophage, and overall redox potential of the epithelial lining fluid in the lung.

The primary null hypothesis is that there will be no difference in alveolar macrophage immune function with zinc treatment, SAME treatment, or combination treatment when compared to placebo in patients with an alcohol use disorder. This will be tested against the alternative hypothesis of a non-zero difference between zinc treatment, SAME treatment, and combination treatment versus placebo. The testing will be done at $\alpha < 0.05$, two-sided, and 80% power to detect a 30% difference between treatment and placebo. Based on our calculations, a total of 100 patients will need to be enrolled (25 in each of the four arms) to ensure adequate statistical power to detect this difference.

2.2 Secondary Aims

[figure not shown]
The primary aim is to determine if there improvement in phagocytic index with zinc treatment, SAME treatment, and combination treatment. An improvement in immune function would signify a decrease in vulnerability to infection. There are other markers of the alcoholic lung phenotype, and these will be used as secondary aims. Specifically, we will examine the effect of zinc, SAME, and combination treatment on alveolar macrophage intracellular zinc levels, redox potential, and GM-CSF receptor expression. The null hypothesis in each of these aims is that zinc, SAME, and combination treatment will have no effect on the above outcomes, with the alternative hypotheses being that treatment will improve intracellular zinc levels, redox potential in the lung, and GM-CSF receptor expression in the alveolar macrophage.

3. Trial Design

3.1 Basic Design

ExZACTO is a single center, double-blind, placebo-controlled, randomized clinical trial to determine the effect of zinc supplementation and SAME supplementation (both alone and in combination) on alveolar macrophage immune function, redox stress, alveolar macrophage GM-CSF reception expression, and intracellular zinc status in outpatient

alcoholic subjects. We will recruit a cohort of otherwise healthy patients with an alcohol use disorder from the Substance Abuse Treatment Program at the Atlanta VA Medical Center and randomize them to one of four treatment groups: 1) usual treatment plus placebo for two weeks; 2) usual treatment plus dietary zinc supplementation for two weeks; 3) usual treatment plus dietary SAME supplementation for two weeks; and 4) usual treatment plus dietary zinc and SAME supplementation for two weeks. The treatment allocation of these studies will be blinded to the patients and investigators. In all, each participant will receive a total of two different pills: 1) zinc placebo and SAME placebo; 2) active zinc and SAME placebo; 3) active SAME and zinc placebo; or 4) active zinc and active SAME. The placebo pills will appear identical to their active drug counterpart. A simple schematic of the study design is depicted below. While the goal of this study to evaluate the effect of two weeks of treatment, in certain instances subjects may receive treatment for longer than two weeks depending scheduling availability for the repeat bronchoscopy. All subjects will remain on treatment from the time of enrollment to the time of repeat bronchoscopy.

3.1.1 Power and sample size calculations

The primary outcome for this clinical trial will be the phagocytic index of the alveolar macrophage before and after at least 14-days of treatment. Phagocytic index is the most relevant primary outcome as it is a well-established marker of immune function and its improvement with either zinc treatment or SAME treatment would indicate reversal of the alcoholic lung phenotype. Secondary outcomes will include change in GM-CSF receptor expression in the alveolar macrophage, change in alveolar macrophage zinc levels (signifying improvement of alveolar zinc deficiency), and change in redox potential [as measured by ratios of the redox couples glutathione/glutathione disulfide (GSH/GSSG) and cysteine/cysteine (Cys/Cyss) in the BAL and EBC fluid].

For the power calculations, we used data from previous animal studies, in which the estimated standard deviation for change in phagocytic capacity is between 0.2 (20%) and 0.40 (40%) depending on baseline values versus follow-up values, respectively. We assume a correlation coefficient of 0.85 between baseline and 14-day follow-up values within a treatment group. Given inherent variability in human data compared to animal data, our assumption will be that the separation of groups will not be as robust. Therefore, we took these predictions, as well as our some of our preliminary data in human subjects, into consideration when calculating sample size requirements. Assuming that we will detect on average a 30% increase in treated (zinc and/or SAME supplemented) subjects and on average no change in the untreated subjects, a sample size of 19 alcoholics in each group will ensure statistical power exceeding 80% to detect a treatment difference of 30% at the 2-sided 5% significance level if the true difference between groups is 30%. However, in order to account for limitations including dropout and inadequacy of sampling, we will use a sample size of 25 subjects in each group (dietary zinc, dietary SAME, and placebo) for a total of 100 subjects randomized for the entire study. This additional recruitment will ensure adequate statistical power is maintained at the completion of the study.

3.1.2 Interim analyses

There are no interim analyses planned as there would be no grounds for stopping the study early for therapeutic benefit. The DSMB will continually monitor the study for any adverse events and will make any determinations for early termination in the unlikely occurrence of harm.

3.1.3 Test statistic for the primary null hypothesis

The primary null hypothesis will be tested in an intent-to-treat analysis using ANOVA to compare in phagocytic function across the four treatment groups.

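### The four-group ANOVA is a valid test of the joint null, but no planned analysis says which treatment differs from placebo or how 5% is held across those claims

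*Combined protocol and SAP*

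**What the plan says.** Section 2.1 (Primary Aim) states one primary null: "no difference in alveolar macrophage immune function with zinc treatment, SAME treatment, or combination treatment when compared to placebo". It sets this against an "alternative hypothesis of a non-zero difference between zinc treatment, SAME treatment, and combination treatment versus placebo", at two-sided 5%, with "80% power to detect a 30% difference between treatment and placebo". The same section describes the design: "ExZACTO is a four-arm (1:1:1:1), factorial design, placebo-controlled, double-blind randomized clinical trial".

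Section 2.2 restates the aim treatment by treatment: "The primary aim is to determine if there improvement in phagocytic index with zinc treatment, SAME treatment, and combination treatment". Section 3.1.1 says of the phagocytic index that "its improvement with either zinc treatment or SAME treatment would indicate reversal of the alcoholic lung phenotype". It then sizes the trial at 19 evaluable per group (25 randomised) for a 30% treatment difference.

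The analysis is the single sentence in 3.1.3: "The primary null hypothesis will be tested in an intent-to-treat analysis using ANOVA to compare in phagocytic function across the four treatment groups". Section 8, despite its title, covers only data capture and software. No section names a placebo contrast, a factorial main effect, an interaction, a testing order or a multiplicity rule.

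**The concern.** The aim and the power statement are about individual treatments against placebo. The only planned test is an omnibus one. A significant F says that the four means are not all equal, and nothing more. It does not say which treatment differs from placebo, and the difference could even lie between two active arms.

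Followed exactly, the plan can reject its null and still leave unanswered whether zinc, SAMe or the combination helps. The tests behind any such claim, and their error level, would have to be chosen after the trial.

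**Working it through.** **Inputs.** From 3.1.1: effect 0.30 in every treated arm and 0 on placebo; 19 evaluable and 25 randomised per arm; two-sided 5%; SD of change between 0.20 and 0.40; correlation 0.85. The SD actually used is not given, so four values are carried:

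- 0.20 and 0.40, the ends of the stated range.
- 0.253 = √(0.2² + 0.4² − 2 × 0.85 × 0.2 × 0.4) = √0.064. This assumes that 0.2 and 0.4 are the baseline and follow-up SDs.
- 0.316 = √((0.2² + 0.4²)/2) = √0.1. This is an assumption chosen because it returns n = 19.

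The analysis variable is taken to be change in phagocytic index, with pooled error from four equal arms.

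**Step 1: the plan's own 19.** For an unadjusted two-arm t test, the noncentrality is 0.30/(SD × √(2/19)).

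- SD 0.253: 3.66, power 94.5%; 13 per arm would be enough for 80%.
- SD 0.316: 2.92, power 81.2%; 19 per arm needed, which matches the plan.
- SD 0.40: 2.31, power 61.4%; 29 per arm needed.

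The four-group F test also gives 19 near SD 0.33. The stated size therefore fits an unadjusted two-arm comparison but does not prove that one was used.

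**Step 2: what the F test can separate.** Its noncentrality is n × Σ(mean − grand mean)²/SD².

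- All three active arms work (0, 0.3, 0.3, 0.3): grand mean 0.225; sum of squares 0.225² + 3 × 0.075² = 0.0675.
- Only the combination works (0, 0, 0, 0.3): grand mean 0.075; sum of squares 3 × 0.075² + 0.225² = 0.0675.

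The two sums are identical, so power is identical. At n = 19 (3 and 72 df):

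| SD | Noncentrality | F power, either pattern |
|---|---|---|
| 0.20 | 32.06 | 99.8% |
| 0.253 | 20.04 | 97% |
| 0.316 | 12.83 | 84.5% |
| 0.40 | 8.02 | 63% |

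When only the combination works, simulation gives a significant F with no placebo contrast significant even at unadjusted 5% in 0.2%, 2%, 5% and 7% of trials, in the same SD order.

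**Step 3: an informal follow-up.** Suppose unadjusted contrasts followed a significant F; the plan does not state this. With all arms null, a false claim against placebo arises in about 4% of trials, because the F test acts as a gate. When only the combination works, that real effect usually opens the gate, and the two null contrasts are then each tested at 5%. Zinc or SAMe is falsely credited in 8-9% of trials. Dunnett gives about 3.5%, and the closed test described under the fix about 4%.

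**Step 4: per-contrast power once error is controlled.** Effect 0.30. Dunnett critical t is 2.400 at 72 df and 2.387 at 96 df. Closed-test figures are simulated with the four-arm pooled error.

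| SD | 19 per arm: closed / Dunnett | 25 per arm: closed / Dunnett |
|---|---|---|
| 0.253 | 93% / 89% | 98% / 96% |
| 0.316 | 74% / 70% | 87% / 83% |
| 0.40 | 49% / 47% | 64% / 60% |

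For comparison, unadjusted contrasts from the same model at 19 per arm have 95%, 82% and 63%.

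**The case against.** The strongest reply is that 2.1 states one null, and 3.1.3 is headed as the test of that null. No difference for any of the three treatments against placebo means four equal means, which is exactly what the F test examines. That stands. A reader might infer that the primary test is wrong or that its type I error is inflated; the documents support neither.

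A reader might also infer that the plan runs three unadjusted tests, with a family-wise error of about 12.4% when all arms are null. The plan states no such tests. The 8-9% figure likewise needs a follow-up the plan does not describe and a world in which only the combination works. In the plan's own scenario every active arm works, so no false credit can arise.

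In a factorial trial, ANOVA could mean a two-way model. The wording about comparing across four groups points to a one-way test without settling it. A two-way model would still leave the placebo comparisons and the error rule unstated. It would also answer a different question: in the plan's scenario the zinc main effect is (0.3 + 0.3)/2 − (0 + 0.3)/2 = 0.15, with unadjusted power of only 90%, 72%, 53% and 36% across the four SDs at 19 per arm.

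Finally, replacing F with Dunnett is a trade-off. At SD 0.316 and 19 per arm, the power to find any effect is 89% with Dunnett against 84.5% with F in the plan's scenario. It is 71% against 84.5% if only the combination works, and 85% against 94% if only zinc has a main effect. This is a good reason to keep the F test.

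**Conclusion.** The concern holds as a gap after a valid first step. The F test controls 5% for the joint null, but it is the only primary analysis stated, and it cannot deliver the treatment-specific answers that 2.1, 2.2 and 3.1.1 ask for. That F power is the same under two very different truths follows from arithmetic at any SD. The values of about 97% and 84.5% rest on assumed SDs of 0.253 and 0.316. The 8-9% false-credit rate shows what an unstated follow-up could do; it is not a property of the plan.

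The power figures do not show that the trial is too small. The SD relied on is not given, and the preliminary human data that also informed the sizing are not shown. This should be fixed before analysis, and it does not undermine the design.

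**What to change.** In 3.1.3, keep the four-group F test as the first step. Add that the three placebo contrasts named in 2.1 follow from the same model, under a procedure that holds two-sided family-wise error at 5%. One example is a closed test: an arm is declared different from placebo only if the four-group F, both three-group F tests that include that arm and placebo, and the arm's own contrast are each significant at 5%. Dunnett is an acceptable alternative. Report each difference with a confidence interval, say whether the intervals are adjusted, and label the 2×2 main effects and the zinc-by-SAMe interaction as supportive.

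In 3.1.1, state the SD of change relied on and restate per-contrast power at the chosen error level.

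The cost is wording and a less favourable power figure. At SD 0.316, for example, per-contrast power at 19 per arm falls from 82% unadjusted to 74% (closed test) or 70% (Dunnett). It is 87% or 83% if all 25 per arm are evaluable. The power of the planned F test is unchanged, and no added enrolment is proposed.

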7.2 Withdrawal of Consent

Participants who withdraw their consent during the course of the trial will discontinue their study medications and follow-up visits, but they will receive phone-call follow to monitor for adverse events and ensure appropriate safety surveillance.

The primary investigator will retain the right to withdraw a subject for any clinical/safety concerns or non-adherence to study protocol.

8. Data Collection and Statistical Considerations

Demographic data will be collected from patients undergoing initial screening for the study. During the study, we will collect data from enrolled subjects from blood samples, exhaled breath condensate and BAL fluid that are collected. The information collected for this trial will be recorded on Case Report Forms (CRFs) and entered in a web-based database called REDCAP. REDCAP is a secure, HIPAA-compliant, data management software website that requires appropriate VA credentials for access. All data entered in the REDCAP database will reside on VA servers.

For data analysis, the VINCI (VA Informatics and Computing Infrastructure) Workspace will be utilized. The VINCI Workspace will allow the team access to SAS (Statistical Analysis Software) while keeping all data on the VA's secured servers, thereby ensuring Veterans' privacy and data security.

9. Trial Administration

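### The primary test is labelled intent-to-treat but is a plain ANOVA, with no baseline covariate and no rule for randomised participants who lack a usable second lavage

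*Combined protocol and SAP*

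**What the plan says.** The test statistic for the primary hypothesis is one sentence in section 3.1.3: the hypothesis is to be "tested in an intent-to-treat analysis using ANOVA to compare in phagocytic function across the four treatment groups". It does not say whether the analysed variable is the change or the follow-up value, names no covariate, and does not define the intent-to-treat set.

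Section 3.1.1 defines the primary outcome as "the phagocytic index of the alveolar macrophage before and after at least 14-days of treatment", so a participant needs a usable index after treatment to contribute to an ANOVA on change or on follow-up. The same section raises each arm from 19 to 25 "in order to account for limitations including dropout and inadequacy of sampling" and gives no rate for either.

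Section 7.2 says that participants who withdraw consent "will discontinue their study medications and follow-up visits", with telephone contact for safety only. It also lets the investigator withdraw participants for safety or non-adherence. Section 8, the statistical section, gives no rule for missing data. Under section 3.3, randomisation follows the first bronchoscopy and is stratified on current smoking.

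**The concern.** The plan foresees missing outcomes and answers them only with recruitment. Recruiting 25 to keep 19 preserves power. It does nothing if those who are lost differ from those who stay, and differ in different ways between arms. Relapse, tablet intolerance and refusal of a second bronchoscopy are plausible reasons for loss in this population, and each could be related to drinking and to macrophage function.

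Run as written, with nothing added, the ANOVA uses only participants with the outcome present, whatever the label says. It also leaves out the baseline index, which is measured before randomisation and which the plan itself expects to correlate at 0.85 with follow-up. That covariate would both protect against loss related to baseline and sharpen the comparison. At stake are the size of the estimated effect, the error rate of the primary test in unfavourable conditions, and precision in all conditions.

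**Working it through.** **Inputs.** From section 2.1: 5% significance, "two-sided, and 80% power to detect a 30% difference between treatment and placebo". From section 3.1.1: SD "between 0.2 (20%) and 0.40 (40%) depending on baseline values versus follow-up values, respectively", 19 evaluable and 25 randomised per arm, and "We assume a correlation coefficient of 0.85 between baseline and 14-day follow-up values within a treatment group".

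**The plan's sample size.** The root mean square of 0.20 and 0.40 is sqrt((0.04 + 0.16)/2) = 0.316. A two-sample t-test for 0.30 with this SD needs 19 per arm (power 81.2%), so the plan's 19 is reproduced. That route does not use the correlation. With it, the SD of change is sqrt(0.04 + 0.16 − 2 × 0.85 × 0.20 × 0.40) = sqrt(0.064) = 0.253, and power at 19 per arm is 94.5%. Power with 19 completers is therefore not the problem here.

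**Implied allowance.** 1 − 19/25 = 6/25 = 24%, or 24 of 100 randomised.

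**How baseline-related loss biases an unadjusted test.** The slope of follow-up on baseline is 0.85 × 0.40/0.20 = 1.7. If the mean baseline of active-arm completers exceeds that of placebo completers by s, then:
- follow-up values are biased by 1.7 × s;
- change is biased by (1.7 − 1) × s = 0.7 × s;
- a correctly baseline-adjusted comparison is not biased by s.

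**Simulation.** Two arms of 25, about 24% lost in each, at random on placebo and preferentially at low baseline in the active arm (logistic slope 1.5 per baseline SD). The true effect is 0.30, or 0 for type I error.

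| Analysis of completers | Estimate for true 0.30 | Two-sided type I error |
|---|---|---|
| ANOVA on change | 0.337 | 7.5% |
| ANOVA on follow-up | 0.389 | 10.9% |
| Baseline-adjusted | 0.300 | 5.2% |

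These agree with the algebra: 0.037/0.7 gives s of about 0.053, and 1.7 × 0.053 = 0.090, against 0.089 simulated.

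**Range.** For selection slopes from 0.5 to 2 per SD:
- change gives 0.317 to 0.341 (type I error 5.0% to 7.4%);
- follow-up gives 0.338 to 0.401 (5.6% to 12.3%);
- the adjusted model gives 0.298 to 0.302 (4.6% to 5.8%).

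At the mildest slope the inflation is negligible.

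**Same mechanism in both arms.** Bias is within 0.005 in every model. In a separate null simulation with outcome-related loss equal in all arms, type I error was 4.9%.

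**Precision with 19 per arm lost at random.** sqrt(2/19) = 0.324.
- Follow-up: 0.40 × 0.324 = 0.130.
- Change: 0.253 × 0.324 = 0.082.
- Adjusted: 0.40 × sqrt(1 − 0.85²) = 0.211, and 0.211 × 0.324 = 0.068.

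**Loss related to the unobserved response, in active arms only.** With correlations of 0.3, 0.5 and 0.7 between loss and change, the unadjusted completer comparison is biased by 0.032, 0.051 and 0.072, with type I error 6.4%, 8.6% and 14.0%. In a similar scenario a baseline-adjusted completer model was also biased, by about 0.05, with type I error about 11%. Baseline adjustment does not cure this kind of loss.

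**The case against.** Intent-to-treat in the sense of analysing people in the arm assigned is compatible with ANOVA, and ANOVA can be run on imputed data. Section 3.1.3 neither excludes imputation nor says that anyone is dropped. This stands. A reader might infer that the stated method cannot deliver the stated population; the documents do not support that. They leave the handling open.

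The simulated bias is removed by adjusting for baseline among completers alone, so the numbers argue first for the covariate and only second for retaining everyone. This also stands. With a common baseline mean and common slope, a longitudinal model estimates the arm difference as (a1 + 1.7m) − (a0 + 1.7m) = a1 − a0, where m is the baseline mean and the intercepts a1 and a0 come from completers. When all baselines are present, including the lost participants mainly makes the population and the missing-at-random assumption explicit.

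The scenario is one-sided. Treatment is masked (section 3.4), the placebos look identical (section 3.1) and the minimum course is two weeks, so loss that differs between arms is less likely. Masking does not exclude it, because side effects or response can still drive loss.

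Finally, section 3.1.1 states no loss rate, and its allowance also covers inadequate samples, which may be technical and unrelated to arm. Nor is randomisation made conditional on a usable baseline index, so complete baseline data should not be assumed.

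**Conclusion.** The concern holds in this form: the primary analysis is an unadjusted ANOVA under an intent-to-treat label, with no stated handling of missing second lavages, although a better method using data already collected is available. This goes beyond missing detail, because leaving out baseline costs precision under any pattern of loss and exposes the test to bias under some.

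In the scenario where loss depends on baseline in an active arm only, the overstatement is about 0.04 (change) or 0.09 (follow-up) on a target of 0.30, with two-arm type I error about 7% or 11%. This rests on the plan's animal-derived SDs, its correlation of 0.85, 24% loss per arm and an assumed strength of selection. The four-group test was not simulated for this scenario. Where loss follows one mechanism in all arms, bias is about zero and the gain is precision only: SE about 0.07, against 0.08 for change and 0.13 for follow-up.

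Two stronger readings are tempting and should be resisted. The plan does not say that it expects to lose 24%; that figure is only the gap between 19 and 25. Nor does type I error exceed 5% in general; it does so only when loss relates to baseline or outcome differently between arms. The change is worth making, but the gap does not by itself invalidate the trial.

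**What to change.** In section 3.1.3:

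1. Replace the ANOVA with a baseline-adjusted, likelihood-based model including every randomised participant with a usable baseline index, in the arm assigned. One suitable choice is a constrained longitudinal model: baseline and follow-up index as outcomes, a common baseline mean, arm-by-time effects and the smoking stratum.
2. Call the analysis restricted to paired usable lavages a completer analysis.
3. Report missing or unusable second lavages by arm and reason.
4. Add one sensitivity analysis for loss related to unobserved outcome, such as reference-based imputation in which active-arm participants without a second lavage are assumed to change as placebo did. It is needed because the primary model relies on missing at random.

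The cost is a revised paragraph and a few lines of code in SAS, which section 8 already names. No extra participants or procedures are needed. The drawback is reliance on missing at random, which item 4 examines. The wording should be agreed before unblinding, so that the choice cannot depend on the results.
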